## **7.5 Tolerability/acceptability**

Not applicable

## **7.6 Resource utilization**

Not applicable

# **8 Safety monitoring**

## **8.1 Serious adverse event reporting**

To ensure subject safety, the investigator has to report every SAE, regardless of suspected causality, occurring after the subject has provided informed consent and until 30 days after following the last administration of study treatment must be reported to the sponsor (or designated CRO) within 24 hours of learning of its occurrence using the SAE reporting form, and recorded in the CRF.

Any SAEs experienced after this 30 day period should only be reported to the sponsor (or designated CRO) if the investigator suspects a causal relationship to the study drug.

All follow-up information for the SAE including information on complications, progression of the initial SAE and recurrent episodes must be reported as follow-up to the original episode within 24 hours of the investigator receiving the follow-up information. Likewise, queries issued by the sponsor regarding the SAE must be responded to within 24 hours.

An SAE that is considered completely unrelated to a previously reported one must be reported separately as a new event.

Information about all SAEs is collected and recorded on the Serious Adverse Event Report Form. The investigator must assess the relationship to study drug, complete the SAE Report Form in English, and send the completed, signed form within 24 hours to the sponsor. The contact details for SAE reporting are listed in the investigator folder provided to each site.

The original copy of the SAE Report Form and the fax confirmation sheet must be kept at the study site.

Follow-up information must be provided using a new SAE Report Form stating that this is a follow-up to the previously reported SAE. The follow-up information must describe whether the event has resolved or continues, if and how it was treated, whether the blind was broken or not, and whether the subject continued or withdrew from study participation. Each re-occurrence, complication, or progression of the original event must be reported as a follow-up to that event regardless of when it occurs.

If the SAE is not previously documented in the Investigator's Brochure or Package Insert (new occurrence) and is thought to be related to the study drug, the sponsor may urgently require further information from the investigator for Health Authority reporting. The sponsor may need to inform all investigators involved in any study with the same drug that this SAE has been reported. Suspected Unexpected Serious Adverse Reactions (SUSARs) will be collected and reported to the competent authorities and relevant ethics committees in accordance with EU Guidance 2011/C 172/01 or as per national regulatory requirements in participating countries.

## **8.2 Reporting procedures for technical complaints**

Any technical complaint about the study drug needs to be reported to the sponsor within 24 hours of identification of the defect (for details refer to the study drug handling manual). Technical complaints are complaints about an optical, organoleptic, qualitative, quantitative, mechanical or functional defect of a pharmaceutical product or medical device. This may include:

- Any fault of quality and/or effectiveness e.g. particles
- Any fault of the containers and outer packages e.g. surface imperfection, container leakage, broken syringe/plunger, missing contents, device malfunction
- Any fault of the labeling e.g. missing or illegible label
- Any falsification of the medicinal product or device e.g. suspected product mix-up, or tampering.

For reporting of adverse events caused by the defect (if applicable) refer to Section [7.4.7](#).

## **8.3 Reporting of study treatment errors including misuse/abuse**

Medication errors are unintentional errors in the prescribing, dispensing, administration or monitoring of a medicine while under the control of a healthcare professional, subject or consumer (EMA definition).

Misuse refers to situations where the medicinal product is intentionally and inappropriately used not in accordance with the protocol.

Abuse corresponds to the persistent or sporadic, intentional excessive use of a medicinal product, which is accompanied by harmful physical or psychological effects.

Study treatment errors, misuse or abuse will be collected and reported in the CRF AE page irrespective of it being associated with an AE/SAE.

## **8.4      Pregnancy reporting**

To ensure patient safety, each pregnancy in a patient on study drug must be reported to Sandoz within 24 hours of learning of its occurrence. The pregnancy must be followed up to determine outcome, including spontaneous or voluntary termination, details of the birth, and the presence or absence of any birth defects, congenital abnormalities, or maternal and/or newborn complications.

Pregnancy must be recorded on a Pregnancy Form and reported by the investigator to the sponsor. Pregnancy follow-up must be recorded on the same form and must include an assessment of the possible relationship to the Sandoz study drug of any pregnancy outcome. Any SAE experienced during pregnancy must be reported on the SAE Report Form.

## **8.5      Data Monitoring Board**

Not Applicable

# **9           Data review and database management**

## **9.1      Site monitoring**

Before study initiation, at a site initiation visit or at an investigator's meeting, a Sandoz representative or designee will review the protocol and CRFs with the investigators and their staff. During the study, the monitor will visit the site regularly to check the completeness of patient records, the accuracy of entries on the CRFs, the adherence to the protocol and to Good Clinical Practice, the progress of enrollment, and to ensure that study drug is being stored, dispensed, and accounted according to specifications. Key trial personnel must be available to assist the monitor during these visits.

The investigator must maintain source documents for each patient in the study, consisting of case and visit notes (hospital or clinic medical records) containing demographic and medical information, laboratory data and the results of any other tests or assessments. All information on CRFs must be traceable to these source documents in the patient's file. Data not requiring a written or electronic record will be defined before study start and will be recorded directly on the CRFs, which will be documented as being the source data. The investigator must also keep a copy of the signed informed consent form.

The investigator must give the monitor access to all relevant source documents to confirm their consistency with the CRF entries. Sandoz monitoring standards require full verification for the presence of informed consent, adherence to the inclusion/exclusion criteria, documentation of SAEs, and the recording of data that will be used for all primary and safety variables.

Additional checks of the consistency of the source data with the CRFs are performed according to the study-specific monitoring plan. No information in source documents about the identity of the subjects will be disclosed.

## **9.2 Data collection**

Designated investigator staff must enter the information required by the protocol onto the Sandoz CRFs that are printed on 2-part, non-carbon-required paper. Monitors will review the CRFs for completeness and accuracy and instruct site personnel to make any required corrections or additions. The original CRFs are forwarded to the CRO by monitors or by the investigational site, the copy is being retained at the investigational site. Once the CRFs are received by the CRO, their receipt is recorded, the original copy is scanned and forwarded to the responsible data management staff for processing. After scanning the original copy is placed in Central Files.

## **9.3 Medical Monitoring**

Medical Monitoring is the summary of all Medical Review activities performed throughout the entire conduct of the study on different levels by different parties. This is to ensure patients' safety and welfare and consistency of data. Medical Review is performed by CRAs during the Monitoring Visit (PRA), at Data Management/Data Validation (Metronomia), and at the sponsor (Study and Program Management at Sandoz). All tasks comprised to warrant a common understanding of duties and schedules of the respective parties in charge have been laid down in writing and filed in the Trial Master File.

# **10 Data analysis**

The analyses will be described in more detail in Statistical Analysis Plans which will be written for each of the interim analyses as well as for the final analysis.

## **10.1 Analysis sets**

### **10.1.1 Safety analysis set**

The safety analysis set (SAF) will comprise all subjects who receive at least one dose of study medication and had at least one post-baseline safety assessment.

### **10.1.2 Full analysis set**

The full analysis set (FAS) will follow the intent-to-treat-principle and therefore consists of all patients who received at least one dose of study medication.

The assignment of the patients to the respective analysis set will be done prior to each interim and to the final analysis during a specific data review meeting.

## **10.2 Patient demographics/other baseline characteristics**

Descriptive statistics will be used to describe background and demographic variables such as age, weight, and height, and frequency tables will be used to describe the gender and race of the patients.

Relevant medical history and current medical conditions, previous medication, results of laboratory screens, drug tests, and any other relevant information will be listed and summarized using descriptive statistics or frequency tables depending on the type of variable (continuous or discrete).

## **10.3 Treatments (study drug, rescue medication, other concomitant therapies, compliance)**

### **10.3.1 Study drug administration**

The extent of exposure will be analyzed using descriptive statistics. Tables showing descriptive statistics for the dose per kg body weight will be presented by visit to assess the appropriateness of the applied doses.

### **10.3.2 Concomitant medication**

Concomitant medication will be coded according to WHO-DRL and the medications will be tabulated by ATC term.

### **10.3.3 Treatment compliance**

The percentage of medication used compared to the amount prescribed will be analyzed for each visit and the frequency of non-compliant patients (daily dose range <80% or >120%) will be tabulated.

## **10.4 Analysis of safety endpoints**

### **10.4.1 Carbohydrate metabolism**

Fasting plasma glucose and insulin levels will be measured at baseline, at 6 and 12 months, then annually during GH treatment, and at the end of treatment. For each of these visits descriptive statistics will be calculated and presented together with the absolute and relative changes as compared to baseline.

Insulin resistance will be estimated using both the homeostasis model assessment (HOMA) (Matthews et al 1985) and quantitative insulin sensitivity check index (QUICKI) (Katz et al 2000, WHO 2002). The effect of Omnitrope® treatment on HOMA and QUICKI scores, calculated subsequent to each plasma glucose and insulin measurement, will be evaluated at each visit using descriptive statistics for the observed values along with the changes from baseline.

Glycosylated haemoglobin (HbA1C) will be measured at baseline, at 6 and 12 months and then annually during GH treatment, and at the end of treatment. The effect of treatment on the HbA1C levels will also be displayed using descriptive statistics.

An oral glucose tolerance test (OGTT) will be performed at baseline, at 6 and 12 months and then annually during GH treatment, and at the end of treatment.

#### **10.4.2 Immunogenicity**

Subjects will be screened for anti-rhGH antibodies (ABs) at baseline, at 3, 6, 9, 12, 18 and 24 months, then annually during treatment, and at the end of treatment. For each time point the number and percentage of patients with anti-rhGH antibodies (ABs) will be tabulated.

Antibody-induced lack or loss of efficacy will be examined by comparing height outcome data between antibody-positive and antibody-negative subjects.

#### **10.4.3 Safety lab / urine analysis**

Haematology, blood chemistry and urine analysis results will be displayed by visit using descriptive statistics and / or frequency tables depending on the type of variable (continuous or discrete). Shift tables for the number and percentage of clinically significant results will also be provided.

#### **10.4.4 (Serious) Adverse Events / Incidents**

Adverse events will be coded using MedDRA (Version to be determined depending on the time of the analysis). The number and percentage of patients having at least one (serious) adverse event will be tabulated. The (serious) adverse events will be displayed by system organ class and preferred term and the relationship to the study drug, intensities and outcome will be shown in corresponding frequency tables.

Since incidents are qualified as clinical SAEs they are handled in the same way as all other clinical SAEs. A near incident is handled as a clinical SAE in case of seriousness, otherwise as an adverse event.

#### **10.4.5 Vital signs / weight**

The development of the vital signs (blood pressure, pulse) as well as weight and BMI will be analyzed using descriptive statistics for each visit.

#### **10.4.6 Physical examination**

Shift tables for normal / abnormal findings will be presented by body system for each visit versus baseline.

### **10.5 Analysis of efficacy endpoints**

#### **10.5.1 Auxological endpoints**

These are height, height SDS, height velocity and height velocity SDS. These parameters will be monitored at baseline, at every 3 months during GH treatment and at the end of treatment. The effectiveness of treatment in inducing growth will be determined by descriptive statistics of the height at each scheduled visit including a comparison to the height at baseline. Similar analyses will be conducted for the height SDS.

The effectiveness of treatment in accelerating linear growth rate will be determined by analyzing the annual height velocity in cm/year (the difference between two height measurements divided by the time interval between these two measurements multiplied by 365.25) at each scheduled visit and by comparing it to the height velocity determined at baseline using historical data. Similar analyses will be conducted for the height velocity SDS.

Treatment will be considered to be ineffective (leading to drug discontinuation) if HVSDS remains below +1 in the first year of treatment.

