#### **Study design:**

Phase IV, prospective, open label, non-comparative, multicentre trial. Omnitrope® treatment will continue until final height is reached. Treatment should be discontinued after the first year of treatment if the height velocity SDS is below +1. Treatment should be discontinued if height velocity is below 2 cm/year

Measurements of carbohydrate metabolism (in terms of fasting plasma glucose, insulin and HbA1c levels) will be performed throughout treatment. Anti-rhGH antibodies (ABs) will be measured during Omnitrope® treatment. Patients will be monitored for safety and efficacy throughout treatment.

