### **4        Study design**

This study is designed as a phase IV, prospective, open label, non-comparative, multicentre trial. Safety and efficacy will be assessed periodically during treatment.

Treatment should be discontinued after the first year of treatment if the height velocity SDS is below +1. Treatment will continue until final height (height velocity < 2 cm/year, [REDACTED]

[REDACTED] is reached but will be discontinued earlier if medically indicated or if there is inadequate response to treatment.

A summary of the study plan is given below.

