### **6.2 Treatment groups**

There will only be one treatment group.

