## 2.4 Statistical methods planned in the protocol

Analyses planned are described in section 10 of the protocol.

Safety and efficacy endpoints will be summarized descriptively. For all efficacy endpoints mean difference between the baseline visit and all later visits and respective 95% confidence will be provided.

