#### Alignment of final visits

A final visit should be performed for all patients terminating study drug. These visits will be analyzed together with the regularly performed study visits. A final visit will be assigned to the appropriate study visit as follows:

In a first step the respective limit between two visit used for assignment, will be assessed as follows: limit = (Day on which VX [= Visit X] should have been performed - Day on which VX-1 should have been performed)/2. The respective limit was rounded if necessary. Days on which a visit should have been performed according to protocol will be assessed as follows (excluding V0 and V1): Month given in the protocol \*(365.25/12) (i.e. V2 = Day 92, V3 = Day 183, V4 = 274 ...).

In a second step final visits performed between VX-1 and the limit (included) will be assigned to VX-1, final visits performed after the limit and prior to VX will be assigned to VX.

For example: A final visit performed between V3 and V4, will be assigned to V3, if performed at or before Day 229 (= (Day 274 + Day 183)/2 = 228.5 => rounded to 229). If performed after Day 229 and at or before V4, the final visit will be assigned to V4.

If due to the assignment of final visits to regular visits two assessments are available for one visit, the assessment nearest to the day on which the visit had to be performed will be used.

If the final visit was performed on the same day as a regular visit, the regular visit will be used for analysis.

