## 4.6 Analysis of secondary endpoints

### 4.6.1 Efficacy evaluation

Data regarding efficacy endpoints will be summarized by visit. Time trends of means will be presented graphically for the secondary endpoints.

For all endpoints, 95% confidence intervals will be calculated for the mean difference between the baseline visit and all later visits, respectively.

Summary tables, plots, and confidence intervals will be presented by visit for the FAS analysis set as well as by sex and the two Omnitrope formulations (i.e. initially treatment). All summary table stratified by initially treatment will be limited to the visit during the first year of treatment. Plots presenting parameters in SDS will not be presented by sex. No plots by initially treatment will be presented. In summary tables presenting data that is also presented graphically confidence limit for means will be added.

All efficacy analyses will be done by completers (who reached the final height) and total.

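### Change in height velocity from baseline cannot show acceleration of growth at late visits: the cm/year rows show slowing whatever the drug does, and the HV SDS rows carry a bias of unknown size

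*Protocol*

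**What the plan says.** Protocol 10.5.1 sets the criterion: "The effectiveness of treatment in accelerating linear growth rate will be determined by analyzing the annual height velocity in cm/year", taken "at each scheduled visit and by comparing it to the height velocity determined at baseline using historical data". It asks for similar analyses of HV SDS. SAP 2.4 carries this over: "For all efficacy endpoints mean difference between the baseline visit and all later visits and respective 95% confidence will be provided". SAP 4.6.1 repeats it: "95% confidence intervals will be calculated for the mean difference between the baseline visit and all later visits, respectively". The resulting tables are 14.2-1.6.x (HV), 14.2-1.8.x (HV SDS, cross-sectional) and 14.2-1.10.x (HV SDS, peak-centred). Neither document sets a last visit for this comparison or restricts it by pubertal stage. Only the tables by initial formulation are confined to the first year.

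Four other provisions bear on it:
- Protocol 6.2: "There will only be one treatment group".
- Children enter at Tanner stage 1 with HV SDS below 0 (Protocol 5.1.1).
- Treatment ends on the measured outcome. Protocol synopsis: "Treatment should be discontinued if height velocity is below 2 cm/year". Protocol Section 4: "Treatment will continue until final height (height velocity < 2 cm/year", after which the text is blacked out. A separate rule stops children whose HV SDS is below +1 in the first year.
- Final visits are mapped to scheduled visits. SAP 4.1: "These visits will be analyzed together with the regularly performed study visits". Missing efficacy values are not imputed (SAP 4.7).

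**The concern.** HV changes with age even without treatment: it declines through childhood, rises at the pubertal spurt and then falls to zero. A change from a pre-pubertal baseline to a visit near final height therefore mixes normal growth, puberty and selective stopping with any drug effect, and there is no control arm to separate them. Age standardisation helps only as far as a study child's pubertal timing matches the reference, and it does nothing about entry and exit rules that select on HV itself.

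At stake is a secondary objective, efficacy on height parameters; the primary diabetes endpoint is untouched. As written, the final report would attach confidence intervals to an apparent deceleration in cm/year, and to an apparent change in SDS, under a heading that says these comparisons determine effectiveness.

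**Working it through.** **1. Plan's own figure.** There is none to reproduce. Neither document gives an expected HV, an HV standard deviation or an effect size, and the Appendix D reference values are not shown.

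**2. cm/year, from the stopping rule alone.** Let B be baseline HV and V the last HV. A child stopping under the rule has V < 2, and SAP 4.6.1 sets negative HV to 0. So the last change D = V - B satisfies -B <= D < 2 - B.
- B = 2: D < 0.
- B = 4 (assumed): D is from -4 to below -2.
- B = 6 (assumed): D is from -6 to below -4.

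The bound contains no drug term. It takes the HV that triggers stopping to be the HV tabulated. Under SAP 4.1 a final value can also be displaced by a regular visit nearer the planned day.

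**3. Row means with no drug effect.** This was a simulation. Inputs from the documents: entry at HV SDS < 0, exit after HV < 2 with the exit value kept, and two standardisations. Assumed inputs: untreated HV 7 cm/year at age 4, falling 0.32 per year; mean age at peak velocity 14 (boys) and 12 (girls), SD 0.7-1.3 years; HV measurement SD 0.4-1.2 cm/year; entry age 4-7 or 4-10; puberty shifted -1.2 to +0.7 years from the reference. The first-year stop at HV SDS below +1 was not applied. Mean change from baseline, range over scenarios with both the entry and exit rules:

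| | Year 10 | Year 12 |
|---|---|---|
| HV, cm/year | -2.1 to -3.5 | -3.6 to -5.2 |
| HV SDS, cross-sectional | +0.14 to +1.51 | +0.54 to +1.77 |
| HV SDS, peak-centred | -1.83 to +2.40 | +0.90 to +3.90 |

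The base case in cm/year is -2.49 at year 10 and -4.09 at year 12.

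**4. What drives each row (base case).**
- cm/year: without the exit rule the year-12 mean is -4.97; with it, -4.09. Normal growth causes the slowing, and the exit rule makes it smaller by 4.97 - 4.09 = 0.88.
- SDS: the HV SDS < 0 entry rule alone shifts the change by about +0.55 from year 1 (regression to the mean). The exit rule adds about +0.16 (cross-sectional) and +1.1 (peak-centred) at year 12.
- Sign: in all three runs with puberty 1.2 years early, the peak-centred change is negative in years 8-11. With puberty 0.7 years early and no entry rule, the cross-sectional change is -0.22 at year 10.

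**5. Precision, cm/year only.** The nearest count in the documents is 32 children still treated on 31-Dec-2019 (Protocol, Study status). It is not a visit count, so this is an illustration. With an assumed SD of the change of 2 to 2.6 cm/year, the half-width is 1.96 x 2/sqrt(32) = 0.69 to 1.96 x 2.6/sqrt(32) = 0.90. The smallest year-10 slowing above, 2.1, exceeds both, so the interval would exclude 0 with no drug effect.

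**6. Who remains.** The last child was enrolled on 29-Apr-2010, so by 31-Dec-2019 at least 9.67 years had passed for everyone. The 32 still treated are 32/278 = 11.5% of those enrolled, and 25/32 = 78% are boys. If girls total 127 + 7 = 134, boys were (278 - 134)/278 = 52% at entry. The late rows describe a selected subset.

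**7. Year 1, cm/year.** With the entry rule and measurement SD 0.8 the no-drug change is +0.22 to +0.26; with SD 0.4 (early puberty) it is -0.09; without the entry rule (early puberty) it is -0.30. The sign is not determined.

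**The case against.** The strongest reply is that little hangs on these rows. HV is a secondary endpoint in an exploratory study, the SAP calls its summaries descriptive, and no test of HV is planned. The one explicit effectiveness threshold in 10.5.1 is at year 1. The SAP already standardises HV in two ways, splits tables by sex and by completers and total, tabulates pubertal stage by visit, and analyses height SDS throughout. On this view a footnote would do.

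Part of this stands: the stakes are modest, and a label on late rows is much of the remedy. But 10.5.1 says that this comparison determines effectiveness, and the intervals invite that reading. The splits do not cure it. Completers are by definition children who reached final height, so their last rows must show slowing, and a split by sex does not align pubertal timing within sex.

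Three stronger readings are tempting and unsupported:
- A reader might infer that late HV SDS rows always show false acceleration, caused by stopping at HV below 2. The sign is not fixed, and with the cross-sectional score the entry rule contributes more than the exit.
- A reader might infer that the spurious SDS changes would be statistically clear. The half-widths above are in cm/year and do not carry over to SDS.
- A reader might infer that the year-1 cm/year comparison understates a real effect. Regression to the mean pulls the other way, so the net direction is open.

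The blacked-out text in Section 4 may add criteria. If they must hold as well as HV below 2, the bound is unaffected; if they are alternatives, it applies only to children who stop under the HV rule.

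**Conclusion.** The point holds for the late rows. In cm/year, the negative last change of a child who stops at HV below 2 follows from the rule itself for any baseline of 2 cm/year or more. The row means of about -2 to -5 cm/year at years 10-12 rest on assumed growth curves, and only their direction should be relied on. In HV SDS, the late change from baseline is not interpretable as a drug effect: its bias is usually upward, of either sign with the peak-centred score, and of a size the documents do not allow anyone to derive. Early HV SDS changes are not clean either, because entry required HV SDS below 0. The planned late comparisons therefore cannot answer the question that 10.5.1 puts to them.

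**What to change.** In Protocol 10.5.1 and SAP 2.4 and 4.6.1:
- Base the statement on acceleration on HV SDS, not cm/year, at Month 12, before the rule on HV SDS below +1 removes children.
- Report the Month 12 HV SDS level against the reference value of 0 beside the change from baseline, and state that the change includes regression to the mean from the entry rule.
- Show children still at Tanner stage 1 as a sensitivity analysis. Pubertal status is recorded at every visit.
- In Tables 14.2-1.6.x, 1.8.x and 1.10.x, do not use the change from baseline and its interval after Month 12, or at final visits, as evidence on acceleration. Keep HV and HV SDS by visit as description, labelled as reflecting normal growth, puberty and selective stopping.
- Judge longer-term effectiveness on the height SDS analyses already planned.

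Extending the window to Month 24 in Tanner stage 1 children would be a poor substitute. It keeps the entry shift, loses the children stopped after year 1 for poor response, and conditions on a state reached after baseline.

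The cost is wording, a few footnotes and one filter on data already held. The downside is fewer rows with an inferential reading. The treatment stopping rule is not changed.
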